	• Any other serious or uncontrolled medical disorder, active infection, physical exam finding, laboratory finding, or psychiatric condition that in the opinion of the investigator would limit the subjects' ability to complete study requirements or may put the subject at increased risk or compromise interpretability of study results. Note: a history of gallstones or kidney stones are not excluded so long as the condition is not acute within 30 days of dosing.
	Additional Exclusion: Group 2 Cohort, 4 and Group 3 Cohorts 6, SeVG-2, and 8
	
 
Recent (within 3 months) significant medical condition or surgical procedure including myocardial infarction, thoracic laparoscopic procedures, or other significant medical inventions
 
Received >20 mg/day of prednisone or an equivalent dose of glucocorticoid for more than 7 days in the last 90 days prior to dosing day
 

	for an acute or chronic disorder
	Currently receiving dialysis
	Currently anuric
Primary Endpoint:	
 
Determine plasma pharmacokinetics of MB-102 compared to the pharmacokinetics of iohexol in subjects with normal and impaired renal function and a range of skin color types (Groups 1 and 2)
 
To show that the MB-102 transdermal fluorescence measured GFR using the ORFM Brilliance device matches the measured MB-102 plasma GFR (Group
 

Casandawy	3) SATE 14 1 SATE 102
Secondary Endpoints:	• Evaluate the safety and tolerance of MB-102
Endpoints:	• Evaluate the safety of the ORFM devices for the noninvasive transdermal fluorescent detection of MB-102
	• Evaluate the effectiveness of the ORFM devices (QuantumLeap, Radiance and Brilliance) through the comparison of fluorescent measurements versus MB-102 across the three groups of subjects
	Determine the optimum dose of MB-102 for noninvasive measurement
Primary Safety Endpoint:	Adverse events (AEs and serious AEs [SAEs], UADEs)
Statistical Methods and Sample Size	As this is a Pilot Study, no formal calculation of sample size was conducted.
Calculations	Safety will be evaluated as the incidence of AEs and SAEs/UADEs. These will be summarized by cohort and overall.
Time Schedule:	Planned Start of Study: April 2016
i inic schedule.	
	Planned End of Study: Sep 2021

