#### 5 Investigational Plan

#### 5.1 Overall Study Design and Plan

Protocol ORFM Pilot 2 is a pilot, safety and pharmacokinetic study of MB-102 versus iohexol (Groups 1 and 2) and the use of the non-invasive ORFM device in normal and compromised renal function subjects with different skin color types.

Up to 261 subjects are intended to be enrolled across 3 Groups stratified by cohorts:

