#### 5.3 Overview of Study Procedures

### **5.3.1** Groups 1 and 2

Potential subjects will be screened for eligibility within 40 days prior to planned dosing. Following pre-dose procedures to ensure eligibility, two ORFM sensors will be affixed to the subjects in Groups 1 and 2; one on the sternum (all subjects) and a second one on an alternative location which may include the forehead, occipital triangle, pectoralis major, lower hip, upper hip, lower sternum or chin. The subject will then receive MB-102 and iohexol injections. MB-102 will be administered by IV injection over 30 seconds, followed by a 10 mL saline flush IV over 30 seconds. Iohexol will be administered to each subject following the MB-102 administration by IV injection over 30 seconds, followed by a 10 mL saline flush IV over 30 seconds.

PK sampling will be collected pre-dose and at 5, 10, 15, 30, 60, 90, 120, 180, 240, 300, 360, 480, 600 and 720 minutes post-dose.

For the subgroup in Cohort 4 who consent to have extended PK collection, additional PK samples will occur at 960 (16 hours), 1440 minutes (24 hours), 1920 minutes (32 hours), 2400 minutes (40 hours) and 2880 minutes (48 hours) post-dose.

Urine will be collected pre-dose and for the 12 hour duration of PK sampling (and extended out to 48 hours for subjects in the extended PK subgroup) for all subjects in Groups 1 and 2. Aliquots of urine will be collected during each void, and the total volume excreted during the 12 or 48 hour post-dose period will be recorded.

Safety assessments in the form of clinical labs, vital signs, ECGs and adverse event collection will occur during the dosing day.

Within 7 +/- 3 days of dosing, subjects will return to the study center for additional safety follow-up assessments.

#### 5.3.2 Group 3

Potential subjects will be screened for eligibility within 40 days prior to planned dosing. Following pre-dose procedures to ensure eligibility, one ORFM sensor will be affixed to the subject and (in certain subjects) a  $2^{nd}$  sensor (connected to a separate device) may be attached to a  $2^{nd}$  location. Sensor placement locations include: the sternum, the forehead, occipital triangle (side of neck), pectoralis major, lower hip, upper hip, lower sternum or chin. A dose of 4  $\mu$ mol/kg MB-102 will be administered by IV injection over 30 seconds, followed by a 10 mL saline flush IV over 30 seconds.

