#### 9.1.3 Pharmacokinetic Assessments

Pharmacokinetic parameters for MB-102 and iohexol will be calculated using both compartmental and non-compartmental techniques. Data from the patients in Cohort 1 that were used for dose ranging for MB-102 will have their data dose normalized to be consistent with the dose used for the remainder of the study. All pharmacokinetic assessments will be performed using Phoenix WinNonlin (and possibly Phoenix NLME) Build 6.4.0.768.

Non-compartmental analysis (NCA) will be performed on data for both MB-102 and iohexol. The following parameters will be determined:

- Cmax the maximum plasma concentration obtained during the sampling interval
- $T_{max}$  the time at which  $C_{max}$  occurred
- $\lambda_z$  the terminal rate constant will be determined by linear regression of the terminal linear phase of the log plasma concentration-time profile.
- AUClast Area under the plasma concentration-time curve from the time zero to the time of the last quantifiable concentration.
- AUC $_{\infty}$  Area under the plasma concentration-time curve from time zero to infinity. (AUC $_{\infty}$ ) will be calculated as: AUC $_{\infty}$  = AUC $_{last}$  + LQC/ $\lambda_z$  where LQC is the predicted concentration (based on the terminal regression) at the time of the last measurable

concentration.

- $t_{1/2} \lambda_z$  the elimination half-life will be calculated as  $t_{1/2} \lambda_z = \ln(2)/\lambda_z$ .
- Clp Total plasma clearance will be calculated as: Clp = Dose/  $AUC_{\infty}$ .
- CLr Renal clearance will be calculated as: CLr = Ae/ AUClast, where Ae is the cumulative amount of analyte excreted in urine over the sampling interval.

In addition to the NCA analysis described above, a compartmental analysis will be performed separately for each subject's profile. Based on prior data, it is expected that a two compartmental model will provide an adequate fit. In addition, a population fit may also be attempted.

Observed plasma and urine concentrations will be summarized descriptively by time point and agent (MB-102 or iohexol) for all subjects included in the pharmacokinetic analysis. In addition, plots of mean concentrations over time will be provided by agent, including standard error bars around the mean values.

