All derived results for pharmacokinetic parameters will be summarized numerically by agent. For categorical variables, the frequency of subjects will be provided along with the percentage based on the number of subjects with available data. Summaries will be based on observed data (i.e., no missing data will be imputed) and will include all dosed subjects completing all aspects of the study.

An analysis of variance of estimated GFR will be performed taking into account the factors subjects, treatments (MB-102 and iohexol), CKD stage and skin color type.

[figure not shown]
All plasma and urine concentrations will be provided in listings by subject and time point. Any blood measurements obtained outside of the defined windows around the scheduled time point will be identified as protocol deviations. Additionally, pharmacokinetic parameters will be provided in listings sorted by subject.

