## 9.1.7 Determination of Sample Size

This is a pilot study therefore no formal calculation of sample size was performed.

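### Section 9.1.3 pools normal and renally impaired subjects in its concentration and PK parameter summaries, so the mean curve may flatten or rise after 12 h while every subject's level falls

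*Combined protocol and SAP*

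**What the plan says.** Three rules in section 9.1.3 (Pharmacokinetic Assessments) matter here.

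- Plasma and urine concentrations are to be "summarized descriptively by time point and agent (MB-102 or iohexol) for all subjects included in the pharmacokinetic analysis".
- Mean curves against time are drawn separately for MB-102 and iohexol, with standard errors shown, and no other split is mentioned.
- For the parameter tables the rule is again one summary per agent: "All derived results for pharmacokinetic parameters will be summarized numerically by agent".

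These summaries use observed data without imputation. They cover dosed subjects who complete the study, and section 9.1.2 counts completion of the dosing day as completing it, so subjects whose sampling ends at 12 h or earlier stay in.

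CKD stage enters elsewhere: as a factor in the analysis of variance of GFR (9.1.3) and in the summaries of the fluorescence-plasma correlation (9.1.3.1). A breakdown by cohort is promised only for safety (Synopsis).

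The Synopsis sets the Groups 1 and 2 primary endpoint as plasma PK of MB-102 against the "pharmacokinetics of iohexol in subjects with normal and impaired renal function and a range of skin color types (Groups 1 and 2").

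Sampling times are in sections 5.3 and 13. Groups 1 and 2 are sampled to 12 h, except for a Cohort 4 subgroup that continues at 16, 24, 32, 40 and 48 h. In Group 3, Cohort 5 (normal) stops at 8 h. The Sensor Optimization Group, the Sensor Verification Group, Cohort 6 and single-dose Cohort 7 stop at 12 h. Cohorts 8 and 8A run to 48 h, and Cohort 8B to 24 h.

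**The concern.** How long a subject is sampled depends on renal function, which also governs how fast the tracer clears. A mean over whoever was sampled therefore changes composition between 12 and 16 h: normal subjects, nearly cleared, drop out, and only impaired subjects, who still carry tracer, remain. The plotted mean can then level off or rise although no individual's concentration does, and it would suggest a slower terminal phase than the subjects have.

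The parameter tables have a related but separate problem. One mean half-life, AUC or Clp over normal to CKD stage 5 describes neither population named in the endpoint.

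The same rule asks for urine concentrations by time point, but urine is collected whenever the subject voids (6.1, 13.1), so there are no nominal times.

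**Working it through.** **Planned total.** "Up to 261 subjects are intended to be enrolled across 3 Groups stratified by cohorts" (section 5.1). Group 3 is 8 + 8 + 27 + 50 + 24 + 24 = 141, and 60 + 60 + 141 = 261, which agrees. The plan has no sample-size formula to reproduce, and the point does not need one.

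**Contributors per time point** (sections 5.1, 5.3, 5.5.2 and 13, maximum planned sizes):

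| | 12 h normal | 12 h impaired | 16 h (all impaired) |
|---|---|---|---|
| Iohexol (Groups 1-2) | 30 + 20 = 50 | 30 + 40 = 70 | 10 |
| MB-102 (all Groups) | 30 + 20 + 27 + 25 + 24 = 126 | 30 + 40 + 8 + 25 + 24 = 127 | 10 + 16 + 8 = 34 |

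Section 5.5.2 gives 16 rather than 24 for each of Cohorts 7 and 8. The 12 h mix would then be 118 to 119, practically the same ratio. Normal Cohort 7B subjects have a 24 h MB-102 sample before their second dose (13.6.4) and none at 16 h.

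**Model.** Each subject declines as C(t) = C0 × 2^(−t/h), with the same C0 for all. Section 3.1 gives a normal half-life of about 2 h for MB-102 and says only that it is longer in impairment. Applying 2 h to iohexol, and every impaired value h, are assumptions.

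- Pooled mean at 12 h = [nN × 2^(−12/2) + nI × 2^(−12/h)] / (nN + nI)
- Pooled mean at 16 h = 2^(−16/h)

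**At h = 8 h**, 2^(−6) = 0.0156, 2^(−1.5) = 0.3536 and 2^(−2) = 0.2500.

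- Iohexol at 12 h: (50 × 0.0156 + 70 × 0.3536) / 120 = 21.3% of C0. At 16 h: 25.0%, a rise of 18%.
- MB-102 at 12 h: (126 × 0.0156 + 127 × 0.3536) / 253 = 18.5%. At 16 h: 25.0%, a rise of 35%.
- Each impaired subject falls from 35.4% to 25.0%.

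**At h = 4 h** there is no rise: iohexol goes from 7.9% to 6.3% and MB-102 from 7.1% to 6.3%.

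**Threshold.** Setting the two means equal gives h = 5.6 h for iohexol (5.3 to 6.2 h for normal half-lives of 1.5 to 2.5 h) and 4.6 h for MB-102 (4.2 to 5.2 h).

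**Varying GFR** (assumed). GFR was drawn uniformly: 60-120 in normal subjects, 15-59 in Cohort 2, and from 5, 10 or 15 up to 59 in the other impaired cohorts. Half-life was 2 h × Gref/GFR with Gref 90, 100 or 120, in 4,000 simulated trials per setting. The pooled mean rose from 12 to 16 h in 52-87% of trials for iohexol and 89-99.9% for MB-102.

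**Remedies in the same simulation.** With impaired subjects only (Gref 100, GFR from 10), the iohexol mean falls from 26.6% to 19.8%. A rise still occurs in about 6% of trials (0.6% to 19% over the settings), because most impaired subjects also stop at 12 h. With the same subjects at both times, a rise occurs in 0% of trials.

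**Parameter means.** With half-lives of 2 h in 50 subjects and 8 h in 70, the pooled mean is (50 × 2 + 70 × 8) / 120 = 5.5 h, which is nobody's half-life.

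**The case against.** Several objections stand and limit the point.

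- **A rise is not established.** A reader might infer that the plan will produce a spurious late rise for both agents. The documents give neither the impaired half-life nor the GFR distribution of the ten extended subjects, so they do not support that. In a two-compartment illustration (assumed: 320 µmol dose, V1 7 L, V2 10 L, Q 8 L/h, 50 normal subjects with GFR 60-120, 70 impaired with GFR 15-59), the pooled mean goes from 2.79 to 3.07 µM if the ten span GFR 15-59. It falls to 1.77 µM if they lie in 30-59.
- **No planned estimate uses the pooled curve.** Compartmental fits are made per subject, and concentrations and parameters are listed by subject.
- **The primary comparison is not blind to renal function.** It would be too strong to say the endpoint receives only one mean across all CKD stages, since the GFR analysis of variance includes CKD stage.
- **Not all late samples come from impaired subjects.** That holds for iohexol and for the 16 h point. For MB-102 at 24 h, Cohort 7B adds normal subjects who then drop out, a further change of composition.
- **The error bars.** A reader might infer that they would mainly show differences between CKD stages. No calculation supports that, and it is not claimed here.

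It may also be said that the wording does not forbid extra displays by cohort, and that this is a hypothesis-generating pilot. Both are true, but the text states which summaries will be made, and none of those for PK is split by renal function. The protocol leaves only laboratory detail and possible imputation rules to a later analysis plan.

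**Conclusion.** The point holds for the descriptive PK tables and mean plots, and only for those. As written, section 9.1.3 pools subjects from normal function to CKD stage 5, and the contributors change from 120 to 10 (iohexol) or from up to 253 to up to 34 (MB-102) between 12 and 16 h, when only impaired subjects remain. These counts come from the documents.

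The pooled mean may therefore stay flat or rise while every subject declines. Whether it does depends on an impaired half-life the documents do not state: above about 5.6 h for iohexol or 4.6 h for MB-102 it rises, and at 4 h or less it does not. These thresholds assume mono-exponential decline, equal starting levels, one common impaired half-life and a 2 h normal half-life.

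Two parts do not rest on those assumptions. Pooled half-life, AUC and Clp means describe neither population in the primary endpoint, and urine voids have no nominal time points. The 12-to-16 h artefact does not apply to the parameter summaries. The change should be made, but no individual PK estimate is at risk.

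**What to change.** In section 9.1.3:

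1. Summarise concentrations, mean plots and PK parameters by agent and renal group: at least normal to CKD 2 against CKD 3-5, and by stage where numbers allow. Show n at every time point.
2. Show 16-48 h means only in a separate panel restricted to the extended-sampling subjects, including their own 0-12 h data. Do not join means across a change in contributors. This is needed as well as item 1, because a renal split alone does not remove the artefact.
3. Summarise urine by collection interval or cumulative amount. The cumulative amount is already derived for CLr.

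The cost is a change of wording and a few more tables and panels, with no new data. The drawback is small n per group at late times: ten extended subjects for iohexol, so a split by stage may leave only a few in each.

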## 6.7 Follow-up Visit

Subjects will return for a safety follow-up visit approximately 7 +/-3 days after dosing. The following assessments will be performed

- Obtain laboratory tests including chemistry, lipids, hematology and urinalysis [and pregnancy test for WOCBP], (Section 7.1.2.6 and Table 8).
- Perform a full or limited physical exam and collect vital signs including temperature (Sections 7.1.2.7 and 7.1.2.8)
- Record concomitant medications
- Collect adverse events

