#### 9 Statistical Methods

# 9.1 Statistical and Analytical Plans

# 9.1.1 Datasets or Populations Analyzed

**Safety Analysis Set:** The Safety Analysis Set (SAF) will consist of all subjects who sign the Informed Consent and receive study drug in the study. All safety analyses will be performed on the safety analysis set.

**Per Protocol Set:** The Per Protocol Set (PP) will consist of all subjects who receive the investigational drug and have no major protocol deviations. Demographic and Other Baseline Characteristics including Subject's age, race, sex, weight, body mass index (BMI), baseline CKD status, and medical history will be recorded at screening and summarized for the Safety and Per Protocol Sets.

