## 9.1.2 Subject Disposition

The number and percentage of subjects who complete the study or who terminate early from the study and the reasons for early termination will be collected and reported. Subjects will be considered to have completed the study if they complete the dosing day.

The number and percentage of subjects in each analysis population will be presented. Percentages will be based on the number of subjects enrolled.

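### The PK parameter summaries are limited to dosed subjects who complete every aspect of the study, a rule that can exclude evaluable plasma profiles and does not match the plan's own definition of completion

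*Combined protocol and SAP*

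**What the plan says.** Section 9.1.3 (Pharmacokinetic Assessments) says that summaries of derived PK parameters use observed data without imputation and "will include all dosed subjects completing all aspects of the study". It does not define what counts as an aspect of the study. Earlier in the same section, concentrations are to be summarised "for all subjects included in the pharmacokinetic analysis".

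Section 9.1.1 defines two sets only. The first is safety: "The Safety Analysis Set (SAF) will consist of all subjects who sign the Informed Consent and receive study drug in the study". The second, Per Protocol, "will consist of all subjects who receive the investigational drug and have no major protocol deviations". Neither is a PK set, and neither requires completion of all aspects.

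Section 9.1.2 gives the plan's only definition of completion: "Subjects will be considered to have completed the study if they complete the dosing day". The schedule runs beyond that day. Section 6.7 states: "Subjects will return for a safety follow-up visit approximately 7 +/-3 days after dosing". The assessments listed for that visit include no PK draw.

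Section 5.5.7 rules out replacing subjects who were dosed but could not complete assessments, and Section 9.1.8 rules out imputation.

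**The concern.** Whether Cmax, AUC or plasma clearance can be estimated depends on the dose given and the concentrations measured. It does not depend on whether a vital sign, an ECG or a visit a week later took place. A completers-only rule makes inclusion depend on those unrelated items.

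For Groups 1 and 2 the primary endpoint is the plasma PK of MB-102 compared with iohexol, so these summaries carry weight. The protocol expects withdrawals (Section 5.5.6), catheters that need replacing (Section 6.4) and light-headedness from blood collection (Section 8.4). Missing an assessment could therefore be related to how the procedure went for that subject, and a completers-only summary could lean towards those in whom it went smoothly. The interim summary in Section 9.1.5 is meant to support regulatory discussions about the pivotal trial, so its denominator should not be open to interpretation.

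**Working it through.** The plan gives no figure for this point, so there is nothing to reproduce. The check compares the rules and the timing.

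1. **Last PK draw against the follow-up visit.** Planned sampling ends at 480 minutes in Cohort 5 (8 hours), at 720 minutes in the standard Group 1 and 2 schedule (12 hours), and at the latest at "2400 minutes (40 hours) and 2880 minutes (48 hours) post-dose". The earliest permitted follow-up visit is 7 − 3 = 4 days, or 4 × 24 = 96 hours. Every profile is finished before that visit, so missing it costs no PK data. Such a subject is a completer under Section 9.1.2 but is excluded by the literal wording of Section 9.1.3.

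2. **Items within the dosing day.** Section 13.1 lists 14 PK draws, 14 sets of vital signs, 4 ECGs, 1 safety laboratory draw, urine collection and adverse event collection: 14 + 14 + 4 + 1 + 1 + 1 = 35. Of these, 35 − 14 = 21 are not plasma PK draws. Urine collection feeds one listed parameter, CLr, through the amount excreted. The other 20 feed none. The vital signs at 725 minutes and the ECG at 740 minutes come after the last standard draw at 720 minutes.

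3. **Direction.** A subject who completed everything has all scheduled draws, so, assay failures aside, the literal set lies inside the set of subjects with evaluable profiles. Compared with a rule based on evaluability, the stated rule can only remove profiles.

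4. **Section 9.1.2 is not a ready substitute.** If the dosing day means the first day, a subject on a 48-hour schedule counts as complete before sampling ends. That definition concerns disposition and does not test whether a profile is usable.

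5. **Size.** The documents give no rate of missed assessments. One excluded subject among the 120 in Groups 1 and 2 is 1/120 = 0.8%. For scale only, let d be the share of dosed subjects with a usable profile who miss some other aspect, and assume d = 1% to 10%. The expected number excluded is n × d: 1.2 to 12 of 120 in Groups 1 and 2, and 1.4 to 14.1 of the 141 planned for Group 3. This range is an assumption and not an estimate.

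**The case against.** The best evidence against a material loss is in the protocol. The synopsis says Groups 1 and 2 are completed, Section 8.1 says 120 subjects received MB-102 followed by iohexol, and Section 3.3 describes PK findings for all 120. That is a narrative and not the final tables, but nothing in it suggests that any profile was dropped. This stands, and it is why no loss should be claimed for those groups.

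The strict reading can also be called strained. The same paragraph of Section 9.1.3 bases percentages on subjects with available data, and the section flags out-of-window draws as deviations without excluding them. A lenient reader could take all aspects to mean getting through the dosing day, which would remove most of the conflict with Section 9.1.2. That is a fair account of what the authors may have meant, but the words go further. If each dosing-day item must be done, a missed 740-minute ECG still excludes an evaluable profile. Section 9.1.3 does not leave its population to be settled in a separate SAP.

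Three stronger readings are tempting and should be resisted:

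- A reader might multiply a per-item miss rate over the 35 items and report a percentage lost. The documents give no such rate, 14 of the items are PK draws, and all 35 fall on the dosing day, so the result would not measure the gap between Sections 9.1.2 and 9.1.3.
- A reader might infer that pairs are lost from the GFR analysis of variance or from the tGFR comparison with plasma. The sentence governs the PK parameter summaries. The analysis of variance is a separate paragraph, and the tGFR correlation is in Section 9.1.3.1. Neither repeats the restriction.
- A reader might say that urine collection is irrelevant. CLr needs it.

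The listings also retain all concentrations and the PK parameters by subject, so any excluded profile remains visible.

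**Conclusion.** The point holds as a defect in a stated inclusion rule. Followed as written, Section 9.1.3 excludes evaluable profiles for reasons unrelated to PK, departs from the completion definition in Section 9.1.2, and stands beside a reference to a PK analysis population that is defined nowhere. The number affected is undocumented and may be small or nil in Groups 1 and 2. Selection towards smooth procedures is possible but not shown. The effect is confined to the PK parameter summaries. The conclusion rests on the literal wording; if the sponsor intended the lenient reading throughout, what remains is the undefined PK set. In a pilot with no formal sample size calculation this does not threaten the study, but the rule should be corrected before the summaries are finalised.

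**What to change.** In Section 9.1.3, replace the completers phrase with: *will include all dosed subjects with sufficient concentration data to estimate the given parameter (and urine data for CLr); missing a non-PK assessment or the follow-up visit is not a reason for exclusion.* State what counts as sufficient for each parameter. Name this as the PK analysis set in Section 9.1.1 and use it for both the concentration summaries and the parameter summaries in Section 9.1.3. Leave Section 9.1.2 to describe disposition only. List every excluded profile with its reason. For Groups 1 and 2 the sponsor can count now how many subjects, if any, the two rules treat differently.

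The cost is a short text change and one listing. No new data are needed.

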	A subset of subjects in Cohort 7 and 8 (Cohorts 7A, 8A and 8B) will have a second sensor type placed on the pectoralis or sternum. This sensor (the 2-Part Brilliance Sensor) is being tested to evaluate a removable adhesive ring that would allow future re-use of the sensor portion.
Treatment:	Eligible subjects will receive a single dose of MB-102 followed by a single dose of iohexol (Groups 1 and 2). Group 3, Cohorts 5, 6, SOG, SeVG-1, SeVG-2 and Cohort 8 will only receive a single dose of MB-102 and will not receive iohexol. A subset of subjects in Group 3, Cohort 7 will receive 2 doses of MB-102. Blood draws will be taken at pre-defined timepoints and the Optical Renal Function Monitor (ORFM) fluorescent measurements will be collected over an 8 - 12 hour period or up to 24-48 hours in certain cohorts.
	Group 1, Cohort 1 subjects may receive a range of doses of MB-102. Assessments of coefficient of variation will determine dose optimization. Remaining Group 1 subjects and Group 2 subjects will receive the optimized dose.
	Group 3 subjects (cohorts 5, 6, SOG and over half the subjects in the SeVG cohort will receive a single dose of 4 µmol/kg. A subset of the SeVG cohort (approximately 20 subjects who weigh greater than 110 lbs (50 kg) will receive a fixed dose of 7 mL (130 mg) MB-102.
	Cohorts 7 and 8 (regardless of weight) will all receive a fixed dose of 130 mg (7 mL).
	A subset of Group 3 subjects in Cohort 7 will receive 2 doses of MB-102 (fixed dose of 7 mL (130 mg). The 2 nd dose will be administered 12 hours after the first dose. For Cohort 7B, subjects will receive their 2 nd dose 24 hours after the first dose.
	Sensor placement in all subjects from Groups 1 and 2 will be in two different locations. All Group 1 and 2 subjects will have a single sensor placed on the sternum. A second location will be assigned to determine additional sites for fluorescent measurements. Group 3 subjects may have 2-3 different sensors located on different parts of the body. At least one sensor will be on the sternum or pectoralis major.  • Group 1 subjects will have fluorescent measurements performed by the
	
 
Prototype QuantumLeap device.
 
Group 2 subjects will have fluorescent measurements performed by the Prototype Radiance device.
 

	Group 3 subjects will have fluorescent measurements performed by the Prototype Brilliance device.

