In the Pilot 2 Groups 1 and 2, the first blood draw was taken at 5 minutes post administration of MB-102, and the last at 12 hours post administration. The transdermal fluorescence was measured at the sternum and one other location for each subject using the prototype device QuantumLeap and Radiance. For all 120 subjects over the wide range of GFR values, the following were observed:

- A two compartment plasma pharmacokinetic profile
- A high correlation between the MB-102 and iohexol plasma derived GFR values
- A high correlation between the MB-102 plasma and transdermal fluorescence pharmacokinetics

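### Section 9.1.3 names no agreement analysis for MB-102 versus iohexol plasma GFR, and the ANOVA treatment term cannot take its place

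*Combined protocol and SAP*

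**What the plan says.** The Synopsis gives the Groups 1 and 2 primary endpoint as: "Determine plasma pharmacokinetics of MB-102 compared to the pharmacokinetics of iohexol in subjects with normal and impaired renal function". The corresponding analysis is in section 9.1.3: "An analysis of variance of estimated GFR will be performed taking into account the factors subjects, treatments (MB-102 and iohexol"). The remaining factors in that sentence are skin color type and CKD stage. I read the GFR in that sentence as the plasma-derived value, because it must take one value per agent. The section states no hypothesis, alpha, margin, limits of agreement or percentage of subjects within a band.

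Two other outputs in section 9.1.3 bear on the comparison: "All derived results for pharmacokinetic parameters will be summarized numerically by agent" and "Additionally, pharmacokinetic parameters will be provided in listings sorted by subject".

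Section 3.3 reports, as an observation on the 120 subjects of Groups 1 and 2, "A high correlation between the MB-102 and iohexol plasma derived GFR values". Section 9 does not plan that correlation. The correlation planned in section 9.1.3.1 is between fluorescence and MB-102 plasma concentration, so iohexol does not enter it.

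Section 6.5 restricts iohexol to Groups 1 and 2. The Synopsis says of most Group 3 cohorts that they "will only receive a single dose of MB-102 and will not receive iohexol". The Group 3 primary endpoint nevertheless compares transdermal GFR with MB-102 plasma GFR.

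**The concern.** A tracer can be right on average and wrong in most individuals. The treatment term responds only to the average. Scatter of the within-subject difference goes into the error term, where it makes a real bias harder to detect, so a noisier tracer is less likely to be flagged as different from iohexol.

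The 120 pairs are the trial's only direct evidence on how well MB-102 plasma GFR reproduces a recognised GFR measure in one subject. Group 3 then uses MB-102 plasma GFR as its sole reference. If the Groups 1 and 2 report gives means by agent and a treatment p-value, a reader of the Group 3 results cannot tell how much error the reference may carry.

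**Working it through.** The documents state no power, alpha, SD or margin, so there is no figure to reproduce.

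**Inputs from the documents.** 50 subjects with normal function to CKD stage 2 and 60 impaired (section 13.1), plus 10 impaired with extended PK (section 13.2): 50 + 60 + 10 = 120 pairs.

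**Assumptions.** Two-sided alpha 0.05. Iohexol GFR uniform on 60–120 in the 50 and on 10–59 in the 70 (mL/min/1.73 m²). Scatter and bias are shown as ranges.

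**Step 1: what the treatment term tests.** Let d be MB-102 GFR minus iohexol GFR in a subject. CKD stage and skin type are fixed within a subject, so the subject factor absorbs them. Then F(treatment) = t², with t = mean(d) / (SD(d)/√120), and residual mean square = var(d)/2. Fitting the ANOVA to a simulated data set confirmed this: F = 1.8986 and paired t² = 1.8986; residual 64310.5/119 = 540.4 and var(d)/2 = 540.4.

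**Step 2: two tracers on the mL/min scale.** MB-102 GFR = iohexol GFR × (1 + error + bias). Tracer A has errors uniform within ±10% (SD 0.10/√3 = 0.0577). Tracer B has errors of exactly +50% or −50% (SD 0.50).

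- Mean GFR = (50×90 + 70×34.5)/120 = 57.6.
- Mean squared GFR = [50×(90² + 60²/12) + 70×(34.5² + 49²/12)]/120 = 4311; square root 65.7.
- With no bias, SD(d) is 0.0577×65.7 = 3.79 for A and 0.50×65.7 = 32.8 for B. Limits of agreement (±1.96 SD) are about ±7.4 and ±64.
- All of A's subjects and none of B's are within 30% of iohexol.

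Share of 20,000 simulated trials with a non-significant treatment term:

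| True mean bias | Tracer A (within ±10%) | Tracer B (±50%) |
|---|---|---|
| 0 | 94.9% | 94.9% |
| 2% | 8.9% | 93.3% |
| 5% | 0% | 84.4% |
| 10% | 0% | 53.1% |

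Hand check at 5% bias: mean(d) = 0.05×57.6 = 2.88. For A, SD(d) is 4.10 and t centres on 2.88/(4.10/√120) = 7.7. For B, SD(d) is 32.9 and t centres on 2.88/(32.9/√120) = 0.96, well below the critical value of 1.98.

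**Step 3: milder scatter, on the log scale.** Let s be the SD of ln(MB-102/iohexol). Limits of agreement are exp(±1.96s). The share within 15% is Φ(ln 1.15/s) − Φ(ln 0.85/s), and likewise for 30%. The chance of missing a 5% bias comes from a noncentral t with parameter ln(1.05)×√120/s, which is 10.7, 2.67 and 1.78 in the three rows.

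| s | 95% limits of the ratio | Within 15% | Within 30% | 5% bias missed |
|---|---|---|---|---|
| 5% | 0.91–1.10 | 99.7% | 100% | 0% |
| 20% | 0.68–1.48 | 55% | 87% | 24.5% |
| 30% | 0.56–1.80 | 38.5% | 69% | 57.6% |

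The limits and band percentages are for no bias. In all three rows, with no bias, the treatment term is non-significant in 95% of trials.

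**The case against.** The strongest reply is that the agreement information will exist. Subject is a factor, so the residual mean square is var(d)/2; between tracers A and B it differs by (0.50/0.0577)² = 75-fold. The per-subject listings hold every pair. This stands: section 9.1.3 generates what is needed. It does not ask for that information to be reported as agreement, and a listing is not an analysis.

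Second, section 5.5.1 calls the study hypothesis generating, section 5.4 says its data will serve the design of later studies, and the endpoint speaks of comparing pharmacokinetics, not of interchangeability in individuals. That excuses the absence of a pass criterion. It does not favour a test of means over an estimate of agreement; where significance is not the aim, estimates fit better.

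Third, correlation does fall with scatter. In a simulation with GFR 60–130 in the 50 and 10–60 in the 70, r was 0.995, 0.93 and 0.85 at log SDs of 5%, 20% and 30%. So it is not blind to disagreement. But over so wide a GFR range, r of 0.93 goes with only 55% of subjects within 15%.

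A reader might go further and infer any of the following, which the documents do not support:

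- That the ANOVA is the only planned comparison. By-agent summaries and listings are also planned; it is the only inferential one.
- That it returns the same answer whatever the scatter. That needs zero mean bias; Step 2 shows large differences otherwise.
- That the trial cannot show how well MB-102 measures a subject's GFR. The data can show it; the plan does not name the analysis.
- That a non-significant term or a high correlation will be taken as proof of comparability. No section says so.

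Finally, the protocol refers to a statistical analysis plan for laboratory summaries and imputation. Those references do not concern agreement.

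**Conclusion.** The point holds as an omission with a practical consequence. Section 9.1.3 names no agreement analysis for MB-102 against iohexol, and its one inferential comparison cannot substitute for one. The 95% non-significance at zero bias follows from the test itself and held on both the raw and log scales. The rates under bias depend on the assumed scatter: at 5% bias, from 0% missed at a log SD of 5% to 57.6% at 30%, and 84.4% for the extreme ±50% tracer on the raw scale. The documents give no SD, so these figures show a range and do not predict this trial's result. The GFR distribution and alpha are also assumed. This should be corrected: the Groups 1 and 2 comparison supports the only reference used in Group 3, and the pairs are already collected.

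**What to change.** In section 9.1.3, make the main Groups 1 and 2 comparison the within-subject ratio of MB-102 to iohexol plasma GFR. Report:

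- the geometric mean ratio with 95% CI;
- the 95% limits of agreement, each with a CI;
- the percentage of subjects whose MB-102 GFR is within a prespecified band of iohexol GFR, for example 15% and 30%. These cut-offs are my choice, because the documents give none.

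Keep the ANOVA as supportive. When Group 3 is interpreted, cite the SD of the log ratio as the combined measurement error of MB-102 and iohexol; it must not be presented as MB-102 error alone.

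No new subjects or samples are needed. The SD of the log ratio is √(2 × residual mean square) from the same ANOVA on the log scale. With 120 pairs the standard error of each limit is about SD × √(3/120) = 0.16 SD; at a log SD of 20% that gives each limit a CI of about ±1.96×0.16×0.20 = ±0.06 on the log scale, or roughly ±6%. The cost is a paragraph, one table and one plot. The downside is that reported comparability may look less favourable than a correlation or a non-significant p-value would.
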